1.2 Identification and description of the Investigational Medical Device

This information is provided within the Investigator's Brochures (IB) and the Instructions for Use (IFU).

2. CLINICAL INVESTIGATION OBJECTIVES

2.1 Overall Objective

The aim of this clinical trial is to assess the clinical performance and safety of the new medical devices TM Flow and TM Fill in direct restorative treatment (class I and II restorations) polymerized in 3 seconds (3000 mW/cm²) with Bluephase PowerCure.

2.2 Primary Objective

The primary objective is to assess the rate of postoperative hypersensitivity after treatment of class I and II cavities with the new composites TM Flow and TM Fill and to compare to the acceptance level of 10% (see chapter statistics).

2.3 Secondary Objectives

The secondary objective of this study is to assess the long-term clinical efficacy of the materials under investigation in terms of functional (fracture of material and retention, marginal adaptation, proximal contact point, form and contour, occlusion and wear) biological (caries at the restoration margins, dental hard tissue defects at the restoration margin, pulpal status) and aesthetic properties (surface luster and surface texture, marginal staining, colour match). These outcomes provide information about the clinical performance of the material including the aesthetic performance.

2.4 Safety Objectives

This study aims to assess the long-term safety of TM Fill and TM Flow in terms of tooth vitality and failure rate of placed restorations. Tooth vitality is an indicator for the health status of the dental pulp. A vitality test is performed to acquire information about the vitality of teeth. A healthy dental pulp offers a positive response to the vitality test. Once the dental pulp is severely injured an irreversible inflammatory reaction starts with the endpoint the necrosis of the dental pulp. Pulpal necrosis is followed by a negative response to the vitality test.

3. CLINICAL INVESTIGATION OUTCOMES

3.1 Primary Outcome

The primary outcome in this clinical trial is the FDI criteria - B3 pulpal hypersensitivity and pulpal status (Hickel et al. 2022) 1 month after placing of the fillings. FDI grades 3-5 are considered as postoperative hypersensitivity in this clinical investigation, since FDI grade 2 does not need any treatment, subsides spontaneously and does not have further clinical relevance. Postoperative hypersensitivity is considered an indicator of the response of a tooth (pulp) to the therapeutic procedure applied. Postoperative hypersensitivity can be observed within a short time after the treatment. Therefore, it is assessed for the first time at the baseline recall (after 7-10 days). The assessment of postoperative hypersensitivity includes questions about type and duration of pain, intensity of pain and on the stimulus inducing the pain. The subjective perception of the intensity of postoperative hypersensitivity caused by thermal stimuli and caused by occlusal forces (during biting) will be determined by the aid of a Visual Analog Scale (VAS). The VAS values are brought into relationship to the preoperative values. In the table below a description of the correlation between FDI grade and VAS values and clinical signs and symptoms is shown. Not all signs need to be present at one stage. The exact VAS values vary widely from patient to patient, depending on each individual's pain tolerance. Therefore, it is one of the factors influencing the FDI grade, but it is not directly correlated. Not all the described conditions have to be fulfilled to attribute an FDI score. Depending on the intensity and character of the pain, further therapy will be determined. Usually, postoperative hypersensitivity subsides spontaneously and no treatment is necessary. In case of very intense pain an immediate treatment is required. The application of a fluoride varnish is the first procedure of choice. If no improvement is achieved by this method, then the replacement of the restoration would be the next step. In the worst case, the pulp is severely inflamed, requiring endodontic treatment. If the postoperative hypersensitivity does not subside spontaneously or worsens after the applied treatment, the highest assessed FDI value is used for the statistical analysis.

For all participants a 1-month recall is planned to finally assess the postoperative hypersensitivity rate. The clinical experience of the evaluators is of major importance in the correct assessment of the FDI grade. In general, the rule applies, that in case of uncertainties the higher score is attributed.

FDI grade	1	2	3	4	5
Intervention	none	no treatment necessary	fluoride varnish if desired	replacement of restoration or endodontic treatment with access cavity only	endodontic treatment and replacement of restoration
Patient's view / description of pain / discomfort	no complaint	minor pain	distinct pain	persistent pain for prolonged period of time, patient asks for treatment	treatment unavoidable
VAS score	0-3	<5		>5	
Pulp status	none	reversible pulpitis		reversible or irreversible pulpitis	irreversible pulpitis or pulp necrosis, with or without periapical periodontitis
Duration of symptoms	no symptoms	<1 week	>1 week	>1 month	n.a.
Vitality test	normal, short reaction		normal or more intense	intense	negative, nonvital tooth (no response)

The assessment of the pulp status is done at all recalls following the 1-month recall because the pulp is exposed to lifelong stimuli and can react any time. The methods of assessment are as described above. VAS during the 1 year recall and later is only done if the patient feels any hypersensitivity.

3.2 Secondary Outcomes

The FDI criteria are well established parameters to evaluate the long-term performance of dental restorations (Hickel et al., 2022). The following FDI criteria were selected for the evaluations of the fillings in this clinical investigation:

Tooth vitality
A1 - Surface lustre and texture
A2 - Marginal staining
A3 - Color match
F1 - Fracture of material and retention
F2 - Marginal adaptation
F3 - Proximal contact point
F4 - Form and contour
F5 - Occlusion and wear
B1- Caries at restoration margins
B2 - Dental hard tissue defects at the restoration margins
M1 - Patients view

Colour match, surface lustre and texture are secondary outcomes that provide information about the aesthetic potential of the material. Surface lustre also proves information about the ability of the material to be polished to a level where plaque accumulation is reduced and the potential of the material to maintain its lustre over time.

The retention/fracture rate of the restorations and the fracture rate of teeth (dental hard tissue defects at the restoration margins) are outcomes that provide information about the clinical performance of the bond of the restoration to the tooth structure and about the strength of the material and its ability to resist to the occlusal forces.

The marginal quality including marginal staining, marginal adaptation, caries at the margins of the restorations provides information about the quality of the bond between tooth structure and the dental composites.

Contact point, contour and form, occlusion and wear are secondary outcomes that provide information about the physical properties of the material and its ability to maintain its form when in clinical use.

The secondary outcomes will be assessed at all recalls.

3.3 Other Outcomes of Interest

Not applicable

3.4 Safety Outcomes

No other specific safety outcomes than the previous described (postoperative hypersensitivity, loss of vitality, loss of restoration, tooth fracture, tooth loss) will be evaluated.

4. CLINICAL INVESTIGATION DESIGN

4.1 General clinical investigation design and justification of design

A single arm, prospective clinical trial is planned with TM Fill in combination with TM Flow, cured in the 3 seconds curing mode (3000mW/cm²). In this high energy curing mode the photons of the curing light activate the initiator, but also create heat which has raised the concern that heat might be transmitted from the cavity to the pulp with the potential risk of pulp damage. TM Flow will be applied as an initial layer of up to 4 mm thickness (A3.5 mm in case of the shade A3.5 plus). The materials also have an exothermic reaction during the light polymerization that adds to the energy output of the lamp, and since the flowable material have a higher exothermal reaction when compared to sculptable materials, the application of an initial layer of flowable material in the maximal layer thickness represents a worst-case with regard to the pulp response to the temperature increase. The materials will be used for the restoration of class I and II cavities in posterior teeth (molars, premolars) since class I and II cavities are the most frequent in the daily practice and are exposed to the highest occlusal forces. This allows the assessment of the performance of the material in its main field of application.

The participants are recruited from the existing patient base of the internal practice of Ivoclar Vivadent AG and are thus employees of the company. No active recruiting measures are taken. Each participant has the right to refuse further participation in the clinical trial at any time.

No participant will receive more than one restoration during the clinical trial. The recruited participants who meet all inclusion criteria will have a detailed medical anamnesis (signed by dentist and participant) to evaluate diseases and a detailed dental medical report. In addition, there is a therapy plan in the sense of the complex rehabilitation concept. These details are documented in the participant file independently of the clinical study.

During the study each participant will receive one TM Filling. The restorations will consist of an initial layer TM Flow of up to 4 mm and a subsequent layer TM Fill.

The procedure for the application of the adhesive Adhese Universal is the "Etch & Rinse (E&R)" technique (previous enamel/dentine etching with phosphoric acid).

5 trained operators will insert 65 indirect restorations, so each operator will perform 13 restorations.

2 trained evaluators will perform the baseline examination (7-10 days) after placement of the restorations, and the following recalls at 1, 6, 12, 24, 36 and 60 months.

4.2 Methods for minimising bias

4.2.1 Randomisation

Not applicable since it is a single arm study.

4.2.2 Blinding procedures

Not applicable since it is a single arm study.

4.2.3 Other methods for minimising bias

This section is not applicable

4.3 Unblinding Procedures (Code break)

Not applicable since it is a single arm study.

5. CLINICAL INVESTIGATION INTERVENTION

5.1 Identity of the medical device under investigation

TM Flow is a flowable, light-curing, radiopaque composite (200% AI) for the direct restorative treatment of anterior and posterior teeth. TM Fill is a sculptable, light-curing, radiopaque composite (200% AI) for the direct restorative treatment of anterior and posterior teeth. TM Fill is also suitable for restoring occlusal surfaces. TM Flow and TM Fill cure with light in the wavelength range of 400–500 nm and can be applied in layers of up to 4 mm.

5.1.1 Experimental Intervention (medical device)

The direct filling therapy of a class I or II with flowable and sculptable composites is an everyday procedure for most dentists. The placement of this kind of filling is part of the basic training during dental medicine study. It is described in textbooks and videos which are freely available.

5.1.2 Control Intervention (standard/routine/comparator)

Not applicable since it is a single arm study.

6. STATISTICAL METHODS

6.1 Hypothesis

The Null Hypothesis (H_0) is that the proportion of postoperative hypersensitivity occurrence after the treatment with the new composites (P_{treat}) is higher than the clinically acceptable 10% (P_0). The Alternative Hypothesis (H_1) states that the proportion of occurring hypersensitivity in this study is less than 10%.

Single-arm study with a one-sided hypothesis:

$$H_0: P_{\text{treat}} \geq 10\%$$

$$H_1: P_{\text{treat}} < 10\%$$

The frequency of postoperative sensitivities calculated in meta-analyses with class I and II cavities vary widely between 1% and 29% (Gordan et al., 2002, Hayashi et al., 2003, Heintze et al., 2012, Arbildo et al., 2020, Reis et al., 2015) because there are many influencing factors that are difficult to standardize between different studies. Factors that influence the development of postoperative hypersensitivities include the depth and size of cavities, removal of the smear layer (adhesive strategy), type of tooth, polymerization technique, gap formation between filling material and dentin, inadequate sealing of dentinal tubules, residual caries, bacterial penetration, contractual stress and level of pain sensation. Based on their experience, the dentists of the internal clinic consider the occurrence of more than 10% postoperative hypersensitivity unacceptable. This level was already chosen for previous studies, e.g. «Klinische Untersuchung des F-Composite 2 Systems in der direkten Füllungstherapie» (BASEC-ID 2017-00904).

6.2 Determination of Sample Size

The sample size calculation was performed by [name] (biostatistician) from the Clinical Trials Unit of the Kantonsspital St. Gallen. Her CV and calculations can be provided upon request.

The power was calculated using PASS Version 21.0.5 (PASS 2021 Power Analysis and Sample Size Software (2021). NCSS, LLC. Kaysville, Utah, USA, [ncss.com/software/pass.](http://ncss.com/software/pass/)).

Using the parameters listed in the table below, a sample size of 61 achieves 82% power to detect a difference ($P_1 - P_0$) of -0.076 using a one-sided binomial exact test with a target significance level of 0.05. Considering a drop-out rate of 5%, it is planned to include 65 patients in this study.

Parameters used for the sample size calculation:

P_0	P_1^*	Difference $P_1 - P_0$	Target alpha	Power	Sample size
0.10	0.024	-0.076	0.05	0.82	61

*Proportion of patients that experienced postoperative hypersensitivity after a direct restorative treatment with already established composites at the study site (internal clinic of Ivoclar Vivadent AG).

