Investigator(s):	
 - [name], [name] - [name], [name] - [name], [name] - [name], [name] - [name], [name] - [name], [name] - [name], [name]
Investigational Site(s):	
This is a single center study.
 
R&D Clinic
 
Ivoclar Vivadent AG
 
[name]
 
[name]
 
Liechtenstein

Statistical considerations:	
The sample size was calculated for a single-arm study design with a one-sided hypothesis (target alpha 5%; power of at least 80%).
 
A one-sided binomial exact test is used to calculate if the probability of postoperative hypersensitivities is lower than 10% (acceptance criterium).

Compliance statement:	
This investigation will be conducted in compliance with the CIP, the current version of the Declaration of Helsinki, ISO14155, ICH-GCP (as far as applicable) as well as all national legal and regulatory requirements.

ABBREVIATIONS

AE	Adverse Event
ADE	Adverse Device Effect
ASADE	Anticipated Serious Adverse Device Effect
ASR	Annual Safety Report
CA	Competent Authority (Amt für Gesundheit Liechtenstein)
CEC	Competent Ethics Committee
CIP	Clinical investigation plan
ClinO	Ordinance on Clinical Trials in Human Research (in German KlinV, in French Oclin, in Italian OSRUM)
ClinO-MD	Ordinance on Clinical Trials with Medical Devices (in German: KlinV-Mep, in French: Oclin-Dim, in Italian: OSRUM-Dmed)
CRF	Case Report Form (pCRF paper CRF; eCRF electronic CRF)
DD	Device Deficiency
DMC / DSMC	Data Monitoring Committee, Data Safety Monitoring Committee
FDI	Fédération Dentaire Internationale
Ho	Null hypothesis
H1	Alternative hypothesis
HRA	Federal Act on Research involving Human Beings (in German: HFG, in French: LRH, in Italian: LRUM)
IB	Investigator's Brochure
ICF	Informed Consent Form
ICH-GCP	International Council for Harmonisation – guidelines of Good Clinical Practice
IFU	Instruction For Use
ISF	Investigator Site File
ISO	International Organisation for Standardisation
ITT	Intention to treat
MedDO	Medical Devices Ordinance (in German: MepV, in French: Odim, in Italian: Odmed)
MD	Medical Device
MDR	Medical Device Regulation (EU) 2017/745 of 5 April 2017
PI	Principal Investigator
SADE	Serious Adverse Device Effect
SAE	Serious Adverse Event
SDV	Source Data Verification

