6.4.1 Datasets to be analysed, analysis populations

The data collected of all eligible participants will be used for the statistical data analysis.

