6.5 Handling of missing data and drop-outs

After baseline drop-outs will not be replaced. In previous clinical trials, there were few drop-outs in the internal clinic of Ivoclar Vivadent AG. There had also been a small number of no-shows.

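### Enrolling 65 to allow for 5% drop-out does not secure the planned power of at least 80%, because 61 is the smallest number scored at which two events still pass the exact test

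*Combined protocol and SAP*

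**What the plan says.** All references are to the combined protocol and SAP.

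- Section 6.2 (Determination of Sample Size) states that "a sample size of 61 achieves 82% power to detect a difference" "of -0.076 using a one-sided binomial exact test with a target significance level of 0.05". Its table gives P0 = 0.10, P1 = 0.024, power 0.82 and sample size 61.
- The same section then allows for losses: "Considering a drop-out rate of 5%, it is planned to include 65 patients in this study".
- The synopsis, under Statistical considerations, describes the calculation as "target alpha 5%; power of at least 80" per cent.
- Section 6.4.1 defines the analysis set: "The data collected of all eligible participants will be used for the statistical data analysis". Section 6.5 adds: "After baseline drop-outs will not be replaced". It gives no rule for filling in a missing score.
- Section 6.4.2 places the final primary analysis at 1 month.

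The number entering the primary test is therefore whatever is scored at 1 month, up to 65. The plan gives power for 61 only, and it does not say how many events the trial may have and still pass.

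**The concern.** Dividing by one minus the drop-out rate assumes that more patients never hurt, and that one loss too many costs only a little power. An exact binomial test on a rare event behaves differently. The permitted number of events moves in whole steps. Between steps, each added patient lowers power, because there is one more chance of an event under the same limit. At a step, one patient fewer removes a permitted event. If 61 lies exactly on a step, the allowance of four leaves no margin below 61 and slightly lowers power above it.

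This is a pivotal study for conformity assessment with a single confirmatory test. A sponsor reading section 6.2 would not learn that a fifth missing 1-month score cuts the permitted events from two to one, or that the target power is then missed by a wide margin.

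**Working it through.** **Inputs.** P0 = 0.10, P1 = 0.024, one-sided exact binomial test, alpha 0.05, 5% drop-out and 65 enrolled (section 6.2); target power of at least 80% (synopsis). A lost patient is taken to have no 1-month score and not to be imputed, since the plan gives no imputation rule.

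**Formulas.** For n scored patients, the pass limit c is the largest whole number with P(X ≤ c | n, 0.10) ≤ 0.05. Power is P(X ≤ c | n, 0.024).

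**Step 1: the plan's own figures.** At n = 61, P(X ≤ 2 | 0.10) = 0.0491, which passes, and P(X ≤ 3 | 0.10) = 0.129, which does not. So c = 2 and power = P(X ≤ 2 | 61, 0.024) = 81.95%, matching the stated 82%. The inflation is 61 / 0.95 = 64.2, rounded up to 65, which also matches.

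**Step 2: the other numbers that may be scored.**

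| Scored at 1 month | Lost from 65 | Pass limit c | P(X ≤ c) at 10% | Power at 2.4% |
|---|---|---|---|---|
| 65 | 0 | 2 | 0.0360 | 79.5% |
| 64 | 1 | 2 | 0.0389 | 80.1% |
| 63 | 2 | 2 | 0.0421 | 80.7% |
| 62 | 3 | 2 | 0.0455 | 81.3% |
| 61 | 4 | 2 | 0.0491 | 82.0% |
| 60 | 5 | 1 | 0.0138 | 57.6% |
| 54 | 11 | 1 | 0.0237 | 62.7% |

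At n = 60, two events give 0.0530, just above 0.05, so only zero or one event passes. The limit is 1 for n = 46 to 60 and 2 for n = 61 to 75. It reaches 3 only at n = 76.

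**Step 3: average over random loss.** Let K be the number lost, K ~ Binomial(65, d). Average power = Σ P(K = k) × power(65 − k). With d = 0.05:

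- P(K = 0) = 3.6%, with power 79.5%.
- P(1 ≤ K ≤ 4) = 74.0%, with power 80.1-82.0%.
- P(K ≥ 5) = 22.5%, with power of about 58%.
- Average power = 75.9%.

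**Step 4: how far this depends on loss by 1 month.** The period of the 5% is not stated, so d is varied as an assumption:

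| Loss by 1 month | P(60 or fewer scored) | Average power |
|---|---|---|
| 0% | 0% | 79.5% |
| 1% | 0.05% | 79.9% |
| 2% | 1.0% | 80.1% |
| 3% | 4.6% | 79.6% |
| 5% | 22.5% | 75.9% |
| 8% | 60.2% | 67.9% |

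**The case against.** The plan's stated arithmetic is right. The 82% is given for 61 and reproduces, 65 is the correct rounding, and the plan claims no power for 65 or for an average over losses. At the loss it expects, 5% × 65 = 3.25 patients, 61 or 62 are scored and power is 82.0% or 81.3%. One to four losses all meet the target, and with no loss the shortfall is half a percentage point, which is immaterial.

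The 5% may also not apply to the primary endpoint. Follow-up runs to 60 months, while the primary analysis is at 1 month. Section 6.5 excludes replacement only after baseline, which suggests that earlier losses may be replaced, and it reports few drop-outs and no-shows in this clinic. Section 4.1 says the participants are company employees treated in-house. Early loss could well be below 5%.

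All of this stands, and it rules out two stronger readings that a reader might infer. One is that the sample size was miscalculated; it was not. The other is that the trial simply has 76% power; that figure needs the whole 5% to be lost, independently, before the 1-month score, which the documents do not say.

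What the objection does not remove is the step at 61. An expected loss of 3.25 is not a guaranteed one, and the allowance gives no protection against the fifth loss, which is the event a drop-out allowance should guard against.

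**Conclusion.** The point holds as a limited one about how power is stated. The inflation from 61 to 65 does not secure at least 80%: the target is met with 61-64 scored, missed trivially with 65, and missed by more than 22 points with 60 (80 − 57.6 = 22.4). How likely the large shortfall is depends on loss by 1 month, which the documents leave open: 22.5% if the full 5% falls in that window, and at most 4.6% if loss is 3% or less. Average power is about 76% in the first case and 79.5-80.1% in the second.

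These figures take the plan's 2.4% and 10% as given, assume independent losses and assume no imputation. The validity of the test is not in question: the exact test keeps the one-sided error at or below 5% at every number scored. A reader might infer that more patients must be enrolled; the point does not require it, provided the power and the pass limit are stated openly.

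**What to change.** Restate the power in section 6.2 and in the synopsis, for example:

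> *With 65 enrolled, power at a true rate of 2.4% is 79.5-82.0% if 61-65 are scored at 1 month and 57.6-62.7% if 54-60 are scored; averaged over independent 5% drop-out before the 1-month score it is about 76% (79.5-80.1% if drop-out by then is 0-3%).*

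In section 6.4.2, add the pass limit that the test implies: at most two events if 61-75 are scored, and at most one if 46-60 are scored.

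The change is to wording only. The test, alpha, endpoint and enrolment stay as they are. The cost is a less favourable stated power; the gain is that the site can see why at least 61 completed 1-month scores matter.
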